**ABBREVIATIONS**

CI	Chief Investigator
CF	Consent Form
cPIS	Child participant information sheet
DGA	Dental General Anaesthesia
NI	[name]
NHS	National Health Service
PI	Principal Investigator
pPIS	Parent/ caregiver Participant Information Sheet
REC	Research Ethics Committee
SOP	Standard Operating Procedure
SB	[name]
TMF	Trial Master File
UDH	University Dental Hospital
UHW	University Hospital of Wales
WA	[name]

## **1. STUDY SUMMARY**

### **Problem**

Dental general anaesthetic (DGA) is used globally as a common treatment service to manage a wide range of oral diseases and problems, most often for children. It is often used to treat problems associated with the development of dental caries which affects an estimated 2 billion people for permanent teeth and 514 million children for primary teeth. population. Although it is acknowledged that repairing or extracting teeth whilst children are asleep does not manage the problem of dental caries or prevent further problems, it is often the only way to provide dental care. This is especially for young children who cannot cope with the invasive nature of dental treatment when they are awake, especially if they have pain or infections associated with the teeth.

There is a large body of literature on its clinical safety. However, despite it being so common, there is little evidence of parents and children's experiences of either dental treatment provided under general anaesthetic (GA) or their experiences of GA itself. The minimal evidence available, suggests poor experiences for children. This presents a risk for parents and children with potentially minimal, or inappropriate information, communication and support needed, failing to meet their needs or being less effective in supporting recovery from this invasive and potentially traumatic event.

### **Aim**

To explore children and their parents' or caregivers' expectations of, experience of, and reflections on, children's DGA in terms of the communication and support provided.

### **Project Plans**

This is a descriptive longitudinal study using a multi-method data-collection, qualitative approach. The data will be collected from the parents/caregivers and their children (six years-old and above) who are undergoing a DGA experience. Data will be collected via in-depth interviews both pre, and post the DGA, complemented by audio diaries which the parents will self-record, around the operation time.

### **Discussion:**

This study will bring in-depth, contemporaneous, directly reported insights into the DGA experiences of children and their parents/caregivers around the most common procedure for hospitalisation of children in the United Kingdom (UK). The findings of this project will provide information to form a building block for wider cross-nation research efforts to improve the DGA experience for children and their parents and inform future work using audio diaries to capture information from patients.

## **2. BACKGROUND AND RATIONALE**

General anaesthesia is a commonly used method to facilitate dental treatment provision for children when the planned care cannot be provided with local anaesthesia or behaviour management techniques alone. This type of anaesthesia, referred to as Dental General Anaesthesia (DGA), is typically conducted by a multi-disciplinary medical and dental team led by specialists or consultants in paediatric dentistry within children's hospitals or dedicated dental hospital theatres. In the UK, DGA services usually provide a range of dental procedures, mainly extractions and restorations, with local anaesthesia and sedation also given. After the DGA course of treatment, children are usually discharged to their general dental practitioner for continuing preventive care.

DGA is the most common reason for UK children to be hospitalized, with around 1-2 children out of every 100 undergoing DGA in England in 2020-2021 (n=22,459 DGA procedures). It is mainly used to manage dental caries, a preventable yet common disease in children. Although DGA is necessary, it is an invasive procedure and can have long-term adverse consequences, such as nightmares and negative memories. Studies of children undergoing GA for other medical conditions have shown that 35% experience separation anxiety for months post-operatively. To mitigate these negative effects, children should be prepared and cared for through well-planned protocols that include providing the right information, effective communication, and adequate follow-up. However, this is not always the case in practice. One study showed that some children undergoing DGA did not know much about the procedure, the venue, or whether their parents would accompany them to the operating theatre. Another English study revealed negative feelings and wide variations in service, environment, and communication across six hospitals from the perspectives of child patients and their parents. There is therefore a need for more research on the communication and support provided to children and their families during DGA, as most existing research focuses on clinical outcomes and quality of life.

### **DATA COLLECTION METHOD FOR THIS PROJECT:**

Exploring the issue of DGA requires data collection methods that reflect the complexity of the process, as DGA involves multiple stakeholders and settings and can take months to complete. Interviews were chosen to provide rich data on the experiences and perceptions of the participants, capturing the influence of context, expectations, and social background on DGA. Interviews were combined with longitudinal audio diaries (LADs) for added insights. LADs provide opportunities for participants to verbalize and share their experiences, thoughts, and interactions with various stakeholders. They are also perceived as a convenient and easy-to-use tool, as participants can record their reflections at any time and place. However, LADs have limitations, such as a lack of control over the data collected and the need for constant reminders and prompts from the research team. As LADs are not a common data collection method in dental research, it is important to capture participants' perceptions of their usability.

---

### **IMPACT**

This project aims to provide information for the formation of a building block for UK-wide research efforts to improve the Dental General Anaesthesia (DGA) experience for children and their parents or carers. It will achieve this by initially providing in-depth and current insights into the journey of children and their parents/carers through audio-recordings of their contemporaneous experiences.

The study will also assess the suitability of audio diaries as a method of capturing the experiences of patients.

### **3. AIMS, OBJECTIVES AND OUTCOMES**

#### **AIMS AND OBJECTIVES:**

##### PRIMARY AIM:

To explore the expectations, experiences, and reflections of children and their parents/carers on the verbal and verbal communication and support provided during DGA.

##### SECONDARY AIMS:

To contribute to wider cross-nation research efforts aimed at improving the DGA treatment pathway in terms of communication and support provided to children and their parents/carers; and

To evaluate the suitability of audio diaries as a data collection method for capturing participants' experiences.

##### STUDY OBJECTIVES:

To gather views from children and their parents/carers on the process leading up to DGA and their expectations of the procedure through interviews prior to DGA;

- To gather data on parents' current perceptions of their child's DGA through longitudinal audio diaries (LADs) during the procedure;
- To gather reflections from children and parents/carers on their DGA experience through interviews following the procedure;
- To gather suggestions from parents/carers and children on how to improve communication and support provided during DGA;
- To identify further gaps in evidence to improve dental care and DGA experience for parents and children; and
- To assess the feasibility of using audio diaries as a means of capturing the lived experiences of parents/carers during the procedure by these stakeholders. The study will also provide information on how best to capture contemporaneous experience of patients and whether audio diaries can adequately fulfil this need.

#### **STUDY POPULATION**

We will identify and recruit children and their parents/ caregivers who are attending Cardiff Dental Hospital, Paediatric Dentistry Department and where the child has treatment planned to be carried out under a DGA as part of their care plan.

- Inclusion criteria - children
  - o between 6-16 years old;
  - o referred by their dentist for DGA assessment and attending for routine or urgent care;
  - o no restriction on their American Society of Anesthesiologists (ASA) score
  - o parent considers that the child can understand enough to communicate verbally (should they choose to) for the interview;
  - o can understand in English or Arabic;

- can provide permission for their parents to participate; and
- can sign an age-appropriate assent form.
- Exclusion criteria - children
  - Inability to understand English or Arabic;
  - Inability or unwillingness to provide permission to parent to take part in the study
- Inclusion criteria - parents/ caregivers
  - can be either the biological, step or adoptive parents, and must live with the child and have legal guardianship;
  - can read and communicate English or Arabic; and
  - can give an informed written consent to participate.
  - Have any type of mobile phones with recorder function
- Exclusion criteria – parents/caregivers
  - Inability to provide valid informed consent.
  - do not have any type of mobile phones with recorder function or any mean of voice recording (potential participant will be excluded from stage 2- longitudinal diary recoding during the operation)
  - Unable to sign the age-appropriate assent form

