#### IDENTIFICATION, SCREENING, AND RECRUITMENT PROCESS

Potential participants who are planned to have DGA will be identified through their clinical notes.

At the beginning of each day, a member of research team who have an honorary contract with Cardiff and Vale University Health Board, or the research dental nurses will screen the clinical notes of the children who plan to have an appointment during the day. The notes of potentially eligible patients will have a reminder about the study placed in them for the clinician to remember to bring them to the attention of the researcher if they are having a GA planned. The clinicians will notify a member of the research team (WA, NI or SB) if a DGA is confirmed, and the operation consent has been signed while attending a dental appointment at the hospital. Potential participants will be screened against the eligibility criteria by a member of the research team who is also part of the clinical team in the clinic (including the research dental nurses) who will introduce the research project to the parent/caregiver, along with explaining the risks and benefits of participating in the study. A copy of the Parent/caregiver Information Sheet (pPIS)(Appendix 2), and a consent form (CF)(Appendix 6) will be given to parent/ caregivers who are interested in participating to take home and read. A copy of the Child Participant Information Sheet (cPIS) (Appendix 3, 4, 5) will also be given for the parent/caregiver to read with the child and discuss the study at home. Three version of the cPIS have been developed to suit the various levels of cognitive abilities of the children. The age specification was deliberately removed from the main text of the cPIS age group for our Patient Information Sheet (PIS). This decision was made in recognition that cognitive abilities can vary among children, regardless of their chronological age. Therefore, we have left it to the discretion of the parent or caregiver to decide which version would suit their child understanding best. An estimation of the age groups was suggested at the footer section as follows:

- Young people: 11–16-year-old
- Young Children: 8–10-year-old
- Younger children 6–7-year-old

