#### **QUALITATIVE DATA**

collection will take place in three stages using two qualitative methodologies:

- **Stage 1: Pre-procedure semi-structured interviews (T1):** This stage will be initiated once the DGA (the informed consent form) has been signed and confirmed. A member of the research team will contact the parent or caregiver to schedule an interview. Interviews will be conducted either in-person in a quiet room within the UDH (University Dental Hospital) premises or virtually via a secure connection using Microsoft Teams software, as preferred by the participants. The interview will involve the parents/caregivers and the child if they are happy to join the interview (optional).

In case of online interviews, a consent form will be sent to the participant's preferred address, along with a free return envelope. Open-ended questions will be used during the interview, guided by an interview protocol (found in the appendix 9). Interviews will be audio recorded using a Dictaphone voice recorder for in-person interviews and the software's built-in recording function for online interviews. These recordings will be saved on the university's secure cloud.

- Stage 2: Longitudinal audio diaries (LADs): Participants who have a phone with a recording function or another means of voice recording will be asked to record their thoughts and reflections up to one week before, during, and up to one week after the operation (T2). Participants will use their mobile phone for recording and then securely send the recordings to the WA (principal investigator's) Cardiff University email address.

A member of the research team will guide participants through the process of recording and sending their diaries. If participants encounter IT difficulties, they will be instructed to contact the research team. If needed, the principal investigator will consult with the university's IT support team for assistance. If participants are unable to send their recordings, the principal investigator will provide a secure link to a OneDrive folder where they can upload their recordings directly to the university's secure cloud. If none of these solutions work, data transfer will take place manually using a cable that connects the phone or recorder to a Cardiff University computer, either during an exit interview or when the participant visits the dental hospital. Participants will be compensated with a £30 voucher for their time.

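### A recorder phone is a whole-study inclusion criterion for parents, yet lacking any recorder excludes them from stage 2 only, so the two rules disagree on who may enter

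*Protocol*

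**What the plan says.** Three statements in the protocol govern recorder access.

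- Study Population, inclusion criteria for parents/caregivers: "Have any type of mobile phones with recorder function". The line names a phone and carries no limit to a stage.
- Study Population, exclusion criteria for parents/caregivers: the criterion applies to those who "do not have any type of mobile phones with recorder function or any mean of voice recording", and the bracketed consequence is "potential participant will be excluded from stage 2- longitudinal diary recoding during the operation".
- Section 4, Qualitative Data, stage 2: "Participants who have a phone with a recording function or another means of voice recording will be asked to record their thoughts and reflections".

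The section on identification, screening and recruitment describes a check at entry: "Potential participants will be screened against the eligibility criteria by a member of the research team". It describes no separate check before stage 2.

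The diaries serve a secondary aim, "To evaluate the suitability of audio diaries as a data collection method for capturing participants' experiences", and a matching objective, "To assess the feasibility of using audio diaries as a means of capturing the lived experiences of parents/carers during the procedure by these stakeholders". The primary aim concerns expectations, experiences and reflections on communication and support. The sampling section plans 10 to 12 parent and child dyads, chosen for maximum variation in clinical, social and personal circumstances.

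**The concern.** An inclusion criterion must be met to enter the study. Read that way, a parent without a recorder phone cannot take part at all. The exclusion list says the same parent loses only the diary stage. Both rules cannot decide entry, and two screeners who each follow the text could reach opposite decisions on the same family.

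Two things are at stake. The first is the composition of the sample for the primary aim. Parents without a suitable device may well differ in social and personal circumstances, which is the variation the sampling plan seeks, and the interviews do not need the parent's device. The second is the diary evaluation. Not having a device is an evident obstacle to keeping an audio diary. If such parents are stopped at entry, that obstacle cannot show among those enrolled.

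**Working it through.** There is no figure in the protocol to reproduce. The sample of 10 to 12 dyads rests on similar qualitative studies, not on a formula. The check is therefore a comparison of the texts.

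**Step 1. Apply each rule to each kind of parent**, all other criteria being met.

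| Parent has | Inclusion line alone | Exclusion line and stage 2 text |
|---|---|---|
| Phone with recorder | Eligible, all three stages | Eligible, all three stages |
| Recorder that is not a phone | Not eligible | Eligible, all three stages |
| No means of recording | Not eligible | Eligible for stages 1 and 3 only |

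The rules agree on the first row only. They differ in scope (whole study against stage 2) and in the device required (a phone against any recorder).

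**Step 2. See which reading the rest of the protocol supports.** The stage 2 invitation is addressed to "Participants who have a phone with a recording function or another means of voice recording", which agrees with the exclusion list. The stage 2 fallback for failed transfers provides for a cable from either a phone or a recorder. The expenses section breaks payment down by stage, which fits participation without a diary. One later sentence in stage 2 does assume that participants record on their mobile phone, so the device definition is not uniform even there.

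**Step 3. Ask whether the primary aim needs the device.** In stages 1 and 3 the study team makes the recording, with a Dictaphone in person or with the meeting software online, and participants may choose to be seen in person at the hospital. A parent's own recorder is not needed for either interview.

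**Step 4. Ask what happens to the diary evaluation.** A parent with no recorder keeps no diary under either reading, so on that account the diaries themselves do not change. What changes is whether such a parent is enrolled and can be counted as someone to whom the diary could not be offered. Under the inclusion line no such parent is enrolled. Under the exclusion line they remain in stages 1 and 3 and can be counted.

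**Step 5. Scale.** One dyad is 1/12 = 8.3% to 1/10 = 10% of the planned sample. The protocol gives no rate of recorder access, so the number of dyads affected cannot be derived; it may be none.

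**The case against.** The strongest reply is that the protocol already settles the matter. The exclusion line says what happens to a parent with no recorder, the stage 2 text agrees, and payment is broken down by stage. The one outlier is a single inclusion bullet, and a screener with the full list sees the qualifying line shortly after it. This makes the intended meaning fairly clear, but it does not remove the fault. The inclusion line still has to be met at entry, nothing says that the exclusion line overrides it, and the device required still differs.

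A reader might go further and infer that the conflict flatters the diary result. The documents do not support that. An upward tilt would need two things: the inclusion line applied to the whole study, and suitability judged against all enrolled dyads. The protocol fixes neither, and it states no uptake rate or threshold that could be inflated. If suitability is judged only among those who start a diary, everyone in that group has a recorder under either reading. The protocol also keeps a screening and recruitment log, which might show why families were turned away, although no use of it in the diary evaluation is described.

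A reader might also infer that each family turned away is a dyad of interview data lost. That does not follow either. Recruitment is purposive up to 10 to 12 dyads, so another family would ordinarily take the place. The possible loss is in the variety of the sample, not in its size. The sampling section also disclaims any aim of statistical representation, so the percentages in the working show scale and do not measure bias.

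**Conclusion.** The contradiction is real and is wrong as written; it is not detail left to a later document. Two groups of parents change status with the reading: those with no recorder, for stages 1 and 3, and those with a recorder that is not a phone, for all three stages. If the inclusion line is enforced, the sample for the primary aim is narrowed without need, against the protocol's own sampling intent, and lack of a device could be hidden as a barrier when diary feasibility is judged.

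The practical size depends on how many approached parents lack a recorder phone and on which line the screeners follow. The protocol gives neither, so the effect may be nil or may touch a small number of dyads in a sample of 10 to 12. The case for changing the text rests on the conflict itself, not on an assumed rate.

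**What to change.** - Delete the phone line from the parent inclusion criteria and the recorder line from the study-level exclusion criteria.
- State the condition once, under stage 2. Suggested wording: *Parents with any means of voice recording are offered the diary; those without take part in stages 1 and 3 only.*
- Bring the later stage 2 sentence on recording by mobile phone into line with that definition.
- State that the report of diary feasibility will give the number of dyads not offered the diary because the parent had no means of recording.

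The cost is a wording amendment, with the sponsor's classification and whatever review follows from it, and one extra count. No new data collection beyond noting recorder access is needed, and the sample size does not change.

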#### **RECRUITMENT METHOD:**

##### SAMPLING:

- A purposive recruitment strategy will be adopted to capture child and parent/ caregivers with a broad range of characteristics. Purposive sampling has been chosen as its aim is not to statistically 'reproduce' the characteristics of the total population, but rather to recruit a group of patients who may reveal important insights into the subject area.
- Recruitment will take a place at the Paediatric Dentistry Department of the Dental Hospital (DH) at University Hospital of Wales (UHW), [name]. We will aim for maximum variation through a sample of 10 to 12 parent/caregiver and child dyad participants whose characteristics include a variety of factors including clinical, social, and personal circumstances. We will achieve this by initially inviting all eligible patients to take part, and as cases accumulate, we will actively seek out participants whose demographics are different to those already recruited.
- A sample size of 10-12 parent/caregiver and child dyads is estimated. This estimate is based on qualitative studies with similar contexts and in the same area of research.

**4. STUDY FLOW AND SCHEDULE**

Study Activity	Dec. 2022 -Feb 2023	March 2023	April 2023	May 2023	June 2023	July 2023	Aug. 2023	Sep. 2023	Oct. 2023	Nov. 2023	Dec. 2023	Jan. 2024
Regulations & approvals	█	█										
Recruitment			█	█	█							
Stage 1: T1 data collection			█	█	█	█	█					
Stage2: LAD data collection				█	█	█	█					
Stage 3: T2 data collection				█	█	█	█	█	█			
Transcription				█	█	█	█	█	█			
Data synthesis					█	█	█	█	█			
Draft report to funders (submit 30/11/23)					█	█	█	█	█	█		
Manuscript write up												
End of study												

